6.6 Dose Modifications for Toxicity

Adverse events (both non-serious and serious) associated with Pembrolizumab exposure may represent an immunologic etiology. These AEs may occur shortly after the first dose or several months after the last dose. Pembrolizumab must be withheld for drug-related toxicities and severe or life-threatening AEs as per Table 8 below. See Section 6.8 for supportive care guidelines, including use of corticosteroids.

Treatment discontinuation for AST, ALT deterioration in participants who present with Grade 2 AST or ALT will be triggered only if AST or ALT increases by greater than or equal to 50% relative to the measurement taken at initiation of systemic treatment (Cycle 1 Day 1) and lasts for at least 1 week.

Toxicity	Hold Treatment For Grade	Timing for Restarting Treatment	Treatment Discontinuation
Diarrhoea/ Colitis	2-3	Toxicity resolves to Grade 0-1	Toxicity does not resolve within 12 weeks of last dose or inability to reduce corticosteroid to 10 mg or less of prednisone or equivalent per day within 12 weeks
	4	Permanently discontinue	Permanently discontinue
AST, ALT, or Increased Bilirubin	2	Toxicity resolves to Grade 0-1	Toxicity does not resolve within 12 weeks of last dose
	3-4	Permanently discontinue (see exception below) ^a	Permanently discontinue
Type 1 diabetes mellitus (if new onset) or Hyperglycaemia	T1DM or 3-4	Hold Pembrolizumab for new onset Type 1 diabetes mellitus or Grade 3-4 hyperglycemia associated with evidence of beta cell failure	Resume Pembrolizumab when participants are clinically and metabolically stable
Hypophysitis	2-4	Toxicity resolves to Grade 0-1. Therapy with Pembrolizumab can be continued while endocrine replacement therapy is instituted	Toxicity does not resolve within 12 weeks of last dose or inability to reduce corticosteroid to 10 mg or less of prednisone or equivalent per day within 12 weeks
Hyperthyroidism	3	Toxicity resolves to Grade 0-1	Toxicity does not resolve within 12 weeks of last dose or inability to reduce corticosteroid to 10 mg or less of prednisone or equivalent per day within 12 weeks
	4	Permanently discontinue	Permanently discontinue
Hypothyroidism		Therapy with Pembrolizumab can be continued while thyroid replacement therapy is instituted	Therapy with Pembrolizumab can be continued while thyroid replacement therapy is instituted

Toxicity	Hold Treatment For Grade	Timing for Restarting Treatment	Treatment Discontinuation

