Infusion Reaction	2 ^b	Toxicity resolves to Grade 0-1	Permanently discontinue if toxicity develops despite adequate premedication
	3-4	Permanently discontinue	Permanently discontinue
Pneumonitis	2	Toxicity resolves to Grade 0-1	Toxicity does not resolve within 12 weeks of last dose or inability to reduce corticosteroid to 10 mg or less of prednisone or equivalent per day within 12 weeks
	3-4	Permanently discontinue	Permanently discontinue
Renal Failure or Nephritis	2	Toxicity resolves to Grade 0-1	Toxicity does not resolve within 12 weeks of last dose or inability to reduce corticosteroid to 10 mg or less of prednisone or equivalent per day within 12 weeks
	3-4	Permanently discontinue	Permanently discontinue
All Other Drug-Related Toxicity ^c	3 or Severe	Toxicity resolves to Grade 0-1	Toxicity does not resolve within 12 weeks of last dose or inability to reduce corticosteroid to 10 mg or less of prednisone or equivalent per day within 12 weeks
	4	Permanently discontinue	Permanently discontinue

Note: Permanently discontinue for any severe or Grade 3 drug-related AE that recurs or any life-threatening event.

^a For participants who begin treatment with Grade 2 AST or ALT at Cycle 1 Day 1 of treatment, if AST or ALT increases by greater than or equal to 50% relative to baseline and lasts for at least 1 week then participants should be discontinued.

^b If symptoms resolve within one hour of stopping IMP infusion, the infusion may be restarted at 50% of the original infusion rate (e.g., from 100 mL/hr to 50 mL/hr). Otherwise dosing will be held until symptoms resolve and the participant should be pre-medicated for the next scheduled dose.

^c Participants with intolerable or persistent Grade 2 drug-related AE may hold study medication at PI/delegate discretion. Permanently discontinue IMP for persistent Grade 2 adverse reactions for which treatment with IMP has been held, that do not recover to Grade 0-1 within 12 weeks of the last dose.

Table 8: Dose Modification Guidelines for Drug-Related Adverse Events

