- Participants should be questioned about compliance with the use of anti-viral agents.

Permanent Discontinuation Criteria for Subjects with Non-overdose Hepatic ECIs

Therapy should also be permanently discontinued for any of the following:

- ALT >20 \times ULN
- Child-Pugh score of ≥ 9 points
- Gastrointestinal bleeding suggestive of portal hypertension (e.g., esophageal or gastric varices)
- New onset clinically detectable ascites
- Encephalopathy
- Recurrence of a severe or life-threatening event, or of any of the laboratory abnormalities listed above, that are presumed to be immune-related.

Other participants may be eligible for treatment interruption (and potential re-start) of Pembrolizumab after discussion with the Sponsor, CI/delegate.

Diagnosis and Management of Non-Overdose Hepatic ECIs

HCC subjects are at risk for a range of complications that can cause hepatic laboratory abnormalities with or without clinical decompensation. Those with a history of chronic HCV or HBV infection also have the potential to experience virologic flares. Immune-related hepatitis has been observed in $\sim 1\%$ of subjects who received Pembrolizumab. The following section provides further guidance on the diagnosis and management of potential hepatic complications among HCC subjects.

a. Hepatitis B Flare

Hepatitis B flares are characterized by rapid elevations of ALT and AST to $>5\times$ ULN and/or $>3\times$ baseline. ALT elevation to $\geq 10\times$ ULN is common. In the absence of hepatic decompensation, ALT/AST elevations are typically isolated (i.e. limited/no elevations of bilirubin/ALP). Participants who are compliant with anti-viral therapy should have continued suppression of HBV DNA at the time of flare; thus, detection of HBV DNA should prompt questioning of subjects for compliance. Laboratory abnormalities secondary to flare are typically observed for 3-5 weeks.

Among participants with HBV, a flare should be considered if this pattern is observed and there is no evidence of an alternative etiology. Guidelines for participants with a diagnosis of HBV flare are as follows:

- Care should be instituted in consultation with a hepatologist.
- For participants who have detectable HBV DNA, re-institute anti-viral therapy.

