- At the time of first detection of HCV RNA, send a specimen for HCV genotyping
- Measure AST, ALT, ALP, Tbil, Dbil, INR weekly
- Measure HCV RNA levels every 2 weeks
- Therapy with HCV anti-viral treatments should be strongly considered.

iii. For both recurrent infection and HCV flare: if ALT returns to normal or Grade 1 (if normal at baseline), or to baseline grade (if Grade 2 at baseline) within 12 weeks, and the participants are clinically stable, participants may restart Pembrolizumab treatment. If these conditions are not met, then Pembrolizumab treatment should be permanently discontinued.

c. Immune-related hepatitis

i. Description: Immune-related hepatitis due to Pembrolizumab should be suspected if any of the following is seen:

- AST or ALT baseline values are less than 2×ULN, and AST or ALT laboratory values increase to $\geq 5\times$ ULN
- Among participants with Day 1 ALT or AST $\geq 2\times$ ULN, levels increase to $>3\times$ the Day 1 level
- AST/ALT >500 U/L regardless of baseline level
- Among participants with Day 1 Tbil levels <1.5 mg/dL: a value of >2.0 mg/dL
- Among participants with Day 1 Tbil levels that are ≥ 1.5 mg/dL: a value of $\geq 2\times$ the Day 1 level
- Total bilirubin >51.3 μ mol/L regardless of baseline level.

Immune-related hepatitis is a diagnosis made after excluding other possible etiologies for the change. Viral flare (if applicable), biliary or vascular obstruction, infection, medications, and alcohol use must be ruled out (see below).

ii. Management

- Interrupt Pembrolizumab treatment and alert the sponsor/CI or delegate as per ECI criteria above for ALT, AST, bilirubin, and hepatic decompensation.
- Start IV corticosteroid (methylprednisolone 125 mg) followed by oral corticosteroid (1-2 mg/kg/day).
- Monitor with biweekly laboratory tests including AST, ALT, Tbil, Dbil, ALP, and INR.
- If symptoms and laboratory tests resolve to Grade ≤ 1 or baseline (if abnormal at baseline), taper steroids over 28 days. Pembrolizumab treatment may be restarted after steroid treatment has been tapered to prednisone ≤ 10 mg/day (or equivalent dose of another agent). Treatment and laboratory results must be documented.

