- If laboratory abnormalities do not resolve within 3 weeks, or steroids cannot be lowered to ≤ 10 mg/day (or prednisone equivalent) within 12 weeks, or participants show evidence of decompensation to Child-Pugh C status or have esophageal or variceal bleeding at any point, treatment must be permanently discontinued. This must be documented.

d. Other Hepatic Events of Clinical Interest

- Infection needs to be ruled out with cultures of blood, urine, and ascites (if possible), as well as chest x-ray and abdominal imaging if relevant. If an infection is found, antibiotics should be started.
- If Tbil is elevated above baseline, magnetic resonance cholangiopancreatography or ultrasound with doppler should be obtained to rule out vascular compromise, biliary obstruction, and/or tumour progression. If biliary obstruction is present, consultation with a gastroenterologist and/or an interventional radiologist should be obtained to see if the obstruction may be relieved.
- A careful review of drugs, including herbal and alternative medications, should be obtained, and alcohol use should be ruled out.

- For all of these cases, participants may resume Pembrolizumab treatment if they are clinically stable after appropriate therapy or discontinue the causative agent, as long as laboratory values have returned to Grade 1 or baseline (if normal or Grade 1 at start) or to baseline grade within 3 weeks.
- Treatment must be permanently discontinued if the participant is off Pembrolizumab therapy for infection, obstruction, or drug/alcohol-related toxicity for more than 3 weeks, or if they have oesophageal bleeding, or become Child-Pugh C at any point.

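### Table 8 and section 6.8.3 give conflicting stop and restart rules for drug-related liver events, and the protocol does not say which governs

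*Combined protocol and SAP*

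**What the plan says.** Section 6.6, Table 8, governs drug-related AST, ALT or bilirubin rises. Grade 2 is held and may restart at Grade 0-1. The permanent stop applies if "Toxicity does not resolve within 12 weeks of last dose". For Grade 3-4 the entry is "Permanently discontinue (see exception below", and the exception is footnote a. It covers only participants with Grade 2 AST or ALT at Cycle 1 Day 1, who stop "if AST or ALT increases by greater than or equal to 50% relative to baseline and lasts for at least 1 week".

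Section 6.8.3 covers hepatic events of clinical interest.

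- Its general list opens "Therapy should also be permanently discontinued for any of the following". The only ALT level listed is above 20 x ULN, and a Child-Pugh score of 9 or more is also listed. Other participants may be interrupted and possibly restarted after discussion with the sponsor or chief investigator.
- Subsection (c), immune-related hepatitis, is entered from AST or ALT of 5 x ULN when the baseline is below 2 x ULN, with separate triggers for raised baselines and for bilirubin. After resolution, "Pembrolizumab treatment may be restarted after steroid treatment has been tapered" to a stated level. No grade limit is attached.
- The permanent-stop sentence in (c) begins "If laboratory abnormalities do not resolve within 3 weeks" and goes on to steroid, Child-Pugh C and bleeding criteria.

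On precedence, section 6.8.1 sends the reader to section 6.6 for dose modification. Section 6.8.1.6 describes 6.8.3 as the comprehensive guidance on hepatic events, and section 6.8.2 sends associated immune-related events of clinical interest to 6.8.3.

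**The concern.** Immune-related hepatitis due to pembrolizumab is by definition drug-related, so one event can fall under both Table 8 and 6.8.3(c). The conflict runs in both directions: Table 8 is stricter on severity and 6.8.3(c) is stricter on duration. Neither can be treated simply as the cautious version of the other.

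Section 1.2.2 names hepatotoxicity as a clinically important safety concern for this study, and safety is the primary endpoint. Section 8.3 summarises adverse events by their effect on study drug, among other things. With up to four sites, the number of hepatic discontinuations could depend partly on which section was followed, and participants in the same state could be managed differently.

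**Working it through.** The plan states no figure to reproduce. The check sets the rules side by side and tests whether they overlap. CTCAE grade limits are not printed in the supplied text. The limits used are assumptions: for AST/ALT, Grade 2 from above 3 to 5 x ULN and Grade 3 above 5 x ULN; for bilirubin, Grade 2 from above 1.5 to 3 x ULN.

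| Drug-related liver event | Table 8 (6.6) | Section 6.8.3 |
|---|---|---|
| Grade 3-4 AST, ALT or bilirubin | Permanent stop, except footnote a | Restart possible under (c); ALT stop listed only above 20 x ULN |
| Grade 2, slow to resolve | 12 weeks from last dose | 3 weeks under (c), clock start not stated |

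**1. Severity.** Take a normal baseline ALT that rises to 8 x ULN and is judged immune-related. Since 8 > 5, it is Grade 3, and Table 8 stops treatment permanently. The same value meets the 5 x ULN entry to 6.8.3(c) and is below 20 x ULN, so 6.8.3 permits restart after resolution and taper.

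Footnote a does not remove the conflict. With a baseline ALT of 4 x ULN, its threshold is 1.5 x 4 = 6 x ULN, sustained for a week. The relative trigger in (c) is above 3 x 4 = 12 x ULN. A rise past 12 x ULN that lasts more than a week but resolves within 3 weeks is a stop under footnote a and may restart under (c).

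Size: section 1.3.2 cites Grade 3-4 AST/ALT rises in about 10-12% of patients on another anti-PD-1 antibody in advanced HCC. If that carried over, 0.10 x 32 = 3.2 and 0.12 x 32 = 3.8, so about 3-4 participants. Section 6.8.3 also gives immune-related hepatitis in about 1% of pembrolizumab recipients, a figure that is not specific to HCC: 0.01 x 32 = 0.3.

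**2. Time limit.** Table 8's 12 weeks applies only to Grade 2. The transaminase triggers in (c) start at 5 x ULN, so the overlap there is slight. For bilirubin it is clear. Table 2 gives the limit of normal as 21 umol/L, and the absolute cut-offs in 6.8.3 are 34.2 and 51.3 umol/L:

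- 34.2 / 21 = 1.63 x ULN
- 51.3 / 21 = 2.44 x ULN

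Both are Grade 2 on the assumed limits. Such an event resolving at week 5 may restart under Table 8 but is a permanent stop under 6.8.3(c).

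Nominal gap: 12 x 7 = 84 days and 3 x 7 = 21 days; 84 - 21 = 63 days = 9 weeks. Only Table 8 states its clock start. If the event is found 21 days after the last dose and the 3-week clock starts then (assumption), Table 8 leaves 84 - 21 = 63 days and (c) leaves 21. The gap is 63 - 21 = 42 days = 6 weeks, or two 21-day cycles.

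**3. Weight of one participant.** 1/32 = 3.1 percentage points of the full sample; 1/6 = 16.7 points of the run-in.

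**The case against.** The strongest reply is that the rules are cumulative. The general list says treatment should also stop, and restart is permitted rather than required, so a site that always stops breaches neither section. That reading is available, but the text does not state it. It would leave the restart path in (c) with little to do for transaminases and would make the 20 x ULN criterion largely redundant.

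Second, sites do not decide alone. Section 6.8.3 requires notification within 24 hours, a hepatology consultation and reporting of every retreatment and discontinuation. Section 6.8.2 requires immediate discussion of Grade 2 or higher immune-related events with the chief investigator or designee. This stands and reduces divergence between sites, but it does not tell those consulted which rule applies.

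Three stronger readings are tempting but not supported.

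- A reader might infer a Child-Pugh contradiction, because (c) speaks of cases where "participants show evidence of decompensation to Child-Pugh C status" and (d) of participants who "or become Child-Pugh C at any point". The general list makes a score of 9 or more sufficient for every non-overdose hepatic event, and nothing permits treatment at 9. The class C wording is redundant, not contrary.
- A reader might size the problem from the transaminase release in up to 45% of participants on a CTLA-4 antibody. Section 1.3.2 calls it transient and says it did not warrant discontinuation.
- A reader might cite the 12-week limits for hepatitis B and C flares. Those concern a different cause. The 12 weeks in the (c) stop sentence itself is a steroid-taper limit.

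Nor is it shown that these rules alter the DLT count or the Part 1 decision.

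**Conclusion.** The concern holds as an internal inconsistency in the current text, on two counts.

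First, Grade 3-4 drug-related AST, ALT or bilirubin is a permanent stop under Table 8, apart from footnote a, but may be restarted under 6.8.3(c). This is the stronger count. It would reach about 3-4 of 32 participants if the cited 10-12% rate carried over and those events were judged immune-related. On the protocol's own 1% figure for immune-related hepatitis, the expected number is about 0.3.

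Second, Grade 2 events, mainly bilirubin, have 12 weeks under one rule and 3 under the other. The gap is 9 weeks nominally and about 6 on the stated clock assumption. The 10-12% rate cannot size this count, because it describes Grade 3-4 events.

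Both counts rest on the assumed CTCAE limits. The absence of a stated precedence rule does not. The Child-Pugh wording is a minor alignment point.

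**What to change.** Reconcile Table 8 with its footnote a, the general discontinuation list in 6.8.3 and subsection 6.8.3(c) into one hepatic hold, restart and stop table. Alternatively, state which section takes precedence for a drug-related liver event. Either way, say from what date each resolution period is counted, and align the Child-Pugh wording in 6.8.3(c) and (d) with the general list. Make the cross-references in 6.8.1, 6.8.1.6 and 6.8.2 point to the governing rule. The sponsor decides the clinical content; this review does not say which limit is right.

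The cost is a wording amendment to the protocol, with no extra participants, visits or data.

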6.9 Diet/Activity/Other Considerations

6.9.1 Diet

Participants should maintain a normal diet unless modifications are required to manage an AE such as diarrhoea, nausea or vomiting.

6.9.2 Contraception

Pembrolizumab may have adverse effects on a fetus in utero. Furthermore, it is not known if Pembrolizumab has transient adverse effects on the composition of sperm. For this trial, male participants will be considered to be of non-reproductive potential if they have azoospermia (whether due to having had a vasectomy or due to an underlying medical condition).

Female participants will be considered of non-reproductive potential if they are either:

(1) postmenopausal (defined as at least 12 months with no menses without an alternative medical cause; in women < 45 years of age a high follicle stimulating hormone (FSH) level in the postmenopausal range may be used to confirm a post-menopausal state in women not using hormonal contraception or hormonal replacement therapy. In the absence of 12 months of amenorrhea, a single FSH measurement is insufficient.);

OR

(2) have had a hysterectomy and/or bilateral oophorectomy, bilateral salpingectomy or bilateral tubal ligation/occlusion, at least 6 weeks prior to screening;

OR

(3) has a congenital or acquired condition that prevents childbearing.

Female and male subjects of reproductive potential must agree to avoid becoming pregnant or impregnating a partner, respectively, while receiving study drug and for 120 days after the last dose of IMP by complying with one of the following:

(1) practice abstinence[†] from heterosexual activity;

OR

(2) use (or have their partner use) acceptable contraception during heterosexual activity.

Acceptable methods of contraception are[‡]:

Single method (one of the following is acceptable):

- intrauterine device (IUD)
- vasectomy of a female subject's male partner
- contraceptive rod implanted into the skin

Combination method (requires use of two of the following):

- diaphragm with spermicide (cannot be used in conjunction with cervical cap/spermicide)
- cervical cap with spermicide (nulliparous women only)
- contraceptive sponge (nulliparous women only)
- male condom or female condom (cannot be used together)
- hormonal contraceptive: oral contraceptive pill (oestrogen/progestin pill or progestin-only pill), contraceptive skin patch, vaginal contraceptive ring, or subcutaneous contraceptive injection

†Abstinence (relative to heterosexual activity) can be used as the sole method of contraception if it is consistently employed as the participants preferred and usual lifestyle. Periodic abstinence (e.g. calendar, ovulation, sympto-thermal, post-ovulation methods, etc.) and withdrawal are not acceptable methods of contraception.

Participants should be informed that taking the IMP may involve unknown risks to the fetus (unborn baby) if pregnancy were to occur during the study. In order to participate in the study participants of childbearing potential must adhere to the contraception requirement (described above) from the day of IMP administration (or 14 days prior to the initiation of study medication for oral contraception) for the duration of the study and for 120 days after the last dose of IMP. If there is any question that a participant of childbearing potential will not reliably comply with the requirements for contraception, that participant should not be entered into the study.

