
Summary of Main Inclusion Criteria
	
In order to be eligible for participation in this trial, the participant must:
 
 1. Be willing and able to provide written informed consent/assent for the trial. 2. Be ≥ 18 years of age on day of signing informed consent. 3. Have a diagnosis of Hepatocellular Cancer (HCC) based on AASLD criteria (Appendix 1). 4. Have at least one uni-dimensional lesion measurable by Computed Tomography (CT)-scan or Magnetic Resonance Imaging (MRI) based on mRECIST criteria. 5. Patients who received prior TACE treatment (conventional or DEB-TACE) are eligible, provided they have at least one previously untreated lesion that is measurable based on mRECIST criteria. 6. Be ineligible for surgical resection or liver transplantation. 7. Have a performance status of 0 or 1 on the Eastern Cooperative Oncology Group (ECOG) Performance Scale 8. Demonstrate adequate organ function 9. Have an overall Child-Pugh score ≤ 7 10. Female subject of childbearing potential should have a negative urine or serum pregnancy. If the urine test is positive or cannot be confirmed as negative, a serum pregnancy test will be required. 11. Women of childbearing potential must be willing to use a highly effective method of contraception as outlined in Section 6.9.2 for the course of the study through 120 days after the last dose of Investigational Medicinal Product (IMP). Note: Abstinence is acceptable if this is the usual lifestyle and preferred contraception for the subject. 12. Sexually active males must agree to use an adequate method of contraception as outlined in Section 6.9.2 starting with the first dose of IMP through 120 days after the last dose of study therapy. Note: Abstinence is acceptable if this is the usual lifestyle and preferred contraception for the subject.

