10. Female subjects of childbearing potential must be willing to use an adequate method of contraception as outlined in Section 6.9.2 – Contraception for the course of the study through 120 days after the last dose of IMP.

Note: Abstinence is acceptable if this is the usual lifestyle and preferred contraception for the subject.

11. Sexually active males must agree to use an adequate method of contraception as outlined in Section 6.9.2- Contraception, starting with the first dose of IMP through 120 days after the last dose of IMP.

Note: Abstinence is acceptable if this is the usual lifestyle and preferred contraception for the subject.

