18. Is pregnant or breastfeeding, or expecting to conceive or father children within the projected duration of the trial, starting from screening through to 120 days after the last dose of IMP.
19. Has received prior therapy with an anti-PD-1, anti-PD-L1, or anti-PD-L2 agent.
20. Has a known history of HIV (HIV 1/2 antibodies).
21. Has received a live vaccine within 30 days of first dose of IMP.

Note: Seasonal influenza vaccines for injection are generally inactivated flu vaccines and are allowed; however intranasal influenza vaccines (e.g., Flu-Mist®) are live attenuated vaccines, and are not allowed.

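### Contraception is tied to the first Pembrolizumab dose, so men have no explicit requirement at doxorubicin TACE and the start date for women is ambiguous

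*Combined protocol and SAP*

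**What the plan says.** The rule appears in three places, with different starting points.

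- **Section 6.9.2 (Contraception).** Both sexes agree to avoid pregnancy "while receiving study drug and for 120 days after the last dose of IMP". The section's closing paragraph gives the start as "from the day of IMP administration (or 14 days prior to the initiation of study medication for oral contraception".
- **Inclusion criteria.** For men, Section 4.1.1 item 11 reads "starting with the first dose of IMP through 120 days after the last dose of IMP" and Trial Summary item 12 reads "starting with the first dose of IMP through 120 days after the last dose of study therapy". For women, Section 4.1.1 item 10 reads "for the course of the study through 120 days after the last dose of IMP", and Trial Summary item 11 says that they "must be willing to use a highly effective method of contraception as outlined in Section 6.9.2 for the course of the study". All four items refer to Section 6.9.2.
- **Exclusion 18 (Section 4.1.2).** Pregnancy, breastfeeding, and expecting to conceive or father a child are barred "starting from screening through to 120 days after the last dose of IMP".

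Section 6.2 names Pembrolizumab as the IMP, and Section 6.12 classes TACE as a non-IMP. Section 6.1 sets the TACE drug as doxorubicin, 60 mg for conventional TACE and 75-150 mg for drug-eluting beads. Sections 3.1.1, 3.1.2 and 5.1 put consent, screening and recruitment before TACE. Pembrolizumab follows at least 30 days after TACE, or at least 45 if the IDSMC recommends the longer interval.

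**The concern.** A start date tied to the IMP leaves out TACE, although TACE is given on study with a cytotoxic drug whose dose the protocol fixes. Read as written, a man has no contraception requirement when he receives intra-arterial doxorubicin or at any time before his first Pembrolizumab dose. A woman has one at TACE if the site takes the duration from criterion 10, but not if it takes the start date from the section that the criterion cites. Sites could therefore give different instructions.

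What is at stake is a participant-safety rule and its consistent use across 1-4 sites. No statistical quantity is involved.

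**Working it through.** There is no plan figure to reproduce. The check compares the texts and does simple date arithmetic.

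**1. Start dates side by side**

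| Text | Applies to | Start | TACE covered? |
|---|---|---|---|
| 6.9.2, agreement sentence | Both sexes | While on study drug | No |
| 6.9.2, closing paragraph | Participants of childbearing potential | First IMP day; 14 days earlier for oral contraception | No |
| 4.1.1 item 11; Trial Summary item 12 | Men | First IMP dose | No |
| 4.1.1 item 10; Trial Summary item 11 | Women | Whole study, citing 6.9.2 | Yes, if the criterion's own duration governs |
| 4.1.2 item 18 | Both sexes | Screening | Yes, but as a bar on pregnancy and intention, not a duty to use contraception |

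**2. Can study drug in 6.9.2 include TACE?** Not readily. The Table 3 footnote ends adverse-event recording 130 days after the last study drug, and Section 7.2 ends it 130 days after the last IMP dose. The two terms are used for the same thing.

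**3. Time after TACE with no explicit requirement, under 6.9.2 and the male criterion**

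- Inputs: minimum interval from TACE to Pembrolizumab of 30 or 45 days (Sections 3.1.1 and 3.1.2); oral lead-in of 14 days (Section 6.9.2).
- Gap = minimum interval: at least 30 or at least 45 days.
- Gap with oral contraception = interval − 14: 30 − 14 = 16, or 45 − 14 = 31. At least 16 or 31 days.
- Section 6.5 adds a 3-day allowance to the 45-day interval, and Section 3.1.1 to the 30-day one. If that is an upper limit, the gaps are 30-33 or 45-48 days, and 16-19 or 31-34 with the oral lead-in. The wording elsewhere is only a minimum, so no firm upper limit follows.

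**4. Do the other safeguards close the gap?**

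- Exclusion 18 concerns status and intention at entry. It sets no method and does not address unplanned conception.
- Section 6.9.2 bars entry "If there is any question that a participant of childbearing potential will not reliably comply with the requirements for contraception", but the requirements meant there carry the start date in question.
- Screening falls in the 28 days before TACE (Section 5.1), so the entry pregnancy test can be 28 days old at TACE. Table 3 shows none at TACE.
- The next test is at most 7 days before Pembrolizumab (Table 3 footnote). With the minimum intervals that is no earlier than 30 − 7 = 23, or 45 − 7 = 38, days after TACE. It can detect a pregnancy but comes after the doxorubicin exposure.

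No other text sets a contraception duty around TACE.

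**The case against.** The strongest reply has four parts.

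- **The female texts can be reconciled.** Criterion 10 can be read as supplying the duration while Section 6.9.2 supplies the acceptable methods. A site reading it that way covers TACE and also satisfies 6.9.2. This stands: a reader might infer a flat contradiction for women, and the documents do not support that. What remains is ambiguity, because 6.9.2 lists methods and also states its own, later start.
- **The male rule is consistent.** Both versions of the male criterion agree with 6.9.2. This also stands. For men the point is not an internal conflict but a start date that comes after an on-study cytotoxic treatment.
- **No hazard is documented.** Section 6.9.2 gives its reasons in terms of Pembrolizumab alone, and the documents contain no statement on reproductive risk from doxorubicin. A reader might infer that participants face a demonstrated fetal risk. The documents neither show nor size one. They are also silent on what reproductive advice accompanies standard-of-care TACE, so its absence cannot be assumed.
- **Much is already handled.** Exclusion 18, the entry test, the test before Pembrolizumab and pregnancy reporting (Section 7.2.2) all reduce the exposure. They narrow the gap without imposing contraception at TACE.

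It might also be said that exclusion 18 is the wrong yardstick because it is not a contraception rule. It is used here only to show when the sponsor wanted pregnancy and conception ruled out. Aligning the contraception rule with that window needs no outside standard.

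**Conclusion.** The point holds as a minor one. Section 6.9.2 and the male criterion place the start of contraception after TACE by at least 30 or 45 days, or at least 16 or 31 days with the oral lead-in. Men have no explicit requirement at TACE. For women the start is ambiguous rather than contradictory.

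This rests on reading IMP and study drug as Pembrolizumab only, which Sections 6.2 and 6.12 support, and on the stated minimum intervals. A permitted second TACE could lengthen the time from the first session, but the documents give no date for it, so no figure is attached. The number of participants affected is not given, and the size of the risk cannot be judged. No estimate, analysis set, DLT rule or sample size is affected.

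**What to change.** Change Trial Summary items 11 and 12, Section 4.1.1 items 10 and 11, and both sentences of Section 6.9.2 so that they give one window for both sexes: from screening, matching exclusion 18, and at the latest from the first TACE, through 120 days after the final Pembrolizumab dose. Count the 14-day oral-contraception lead-in back from the first TACE. A woman who cannot meet it uses another method listed in Section 6.9.2.

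The cost is a wording change to the protocol and participant information, and a slightly longer contraception period for participants. If cover from screening is thought too long, starting at the first TACE still removes the gap. No procedure, sample size, DLT rule or analysis changes.
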